**Table JPBQ.10.3. Adverse Event and Serious Adverse Event Reporting Guidelines**

Period	Types of AEs/SAEs to be Reported	Collection Database	Lilly Safety System
Baseline (pretreatment)	Preexisting conditions All AEs SAEs related to protocol procedures	x x x	x
Study treatment period	All AEs All SAEs	x x	x
30-day short-term postdiscontinuation follow-up	All AEs  All SAEs	x  x	x
Long-term postdiscontinuation follow-up	All SAEs related to protocol procedures or study drug	x	x
Continued access period	All AEs All SAEs	x x	x
Continued access period follow-up	All AEs All SAEs	x x	x
After the patient is no longer participating in the study (that is, no longer receiving study therapy and no longer in follow-up)	All SAEs related to protocol procedures or study drug that the investigator becomes aware of		x

Abbreviations: AE = adverse event; SAE = serious adverse event.

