#### **10.3.3.3. Venous Thromboembolic Events**

In the randomized Phase 3 studies in breast cancer patients who received abemaciclib in combination with endocrine therapy, there was a greater number of patients who experienced VTEs in the abemaciclib plus endocrine therapy arm than in the placebo plus endocrine therapy arm. The majority of the events were non-serious and were treated with low-molecular-weight heparin. Generally, these events did not result in discontinuation of the study treatment. At this time, the mechanism underlying the association between abemaciclib and the occurrence of VTEs is not known. For suspected or confirmed VTE (eg. deep vein thrombosis or pulmonary embolism), treatment should occur according to usual clinical practice.

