## 12. Sample Size and Statistical Methods

### 12.1. Determination of Sample Size

The primary objective of this study is to compare abemaciclib plus NSAI versus placebo plus NSAI in terms of PFS in postmenopausal women with HR+, HER2- locoregionally recurrent or metastatic breast cancer.

The key secondary objective of this study is to compare abemaciclib plus fulvestrant versus placebo plus fulvestrant with respect to PFS for postmenopausal women with HR+, HER2- locoregionally recurrent or metastatic breast cancer.

The study plan is to enroll approximately 450 patients in total, with 300 HR+, HER2- locoregionally recurrent or metastatic breast cancer patients who have not received prior endocrine therapy in Cohort A and 150 HR+, HER2- locoregionally recurrent or metastatic breast cancer patients in Cohort B. Assuming approximately 10% screening failure, the study will enter approximately 500 patients.

The approximate 300 patients qualified for Cohort A will be randomized in a 2:1 ratio to Arm A1 (abemaciclib plus NSAI; 200 patients) and Arm A2 (placebo plus NSAI; 100 patients). Patients will be randomized using the following stratification factors: nature of disease (visceral metastases vs. non-visceral metastases) and prior (neo)adjuvant endocrine therapy (prior therapy with disease-free interval > 12 months from completion of treatment vs. prior therapy with disease-free interval ≤ 12 months from completion of treatment vs. no prior therapy).

A 2-look group-sequential design of the primary endpoint will be used to accommodate an event-driven plan for the interim and primary PFS analyses (see Section 12.2.6 for details). The primary PFS analysis will be performed after approximately 170 PFS events in Cohort A have occurred (ie, approximately 43% censoring rate). Assuming a hazard ratio of 0.626, this sample size yields about 81.40% statistical power to detect superiority of the abemaciclib plus NSAI arm over the placebo plus NSAI arm with the use of a 1-sided log-rank test and a type I error of 0.025. If the true median PFS for the placebo plus NSAI arm is 14.4 months, then the hazard ratio of 0.626 amounts to an approximately 8.6-month (59.7%) improvement in median PFS for the abemaciclib plus NSAI arm under an additional assumption of exponential survival distribution.

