### **12.2.12. Safety Analyses**

All safety summaries and analyses will be based upon the Safety Population as defined in Section [12.2.1](#).

Overall exposure to study drug, the numbers of patients completing each cycle, and the dose intensity will be summarized using descriptive statistics. The number of patients with any dose adjustment will be presented for the entire treatment period as well as for each cycle. The number of patients with dose reductions, delays, or omissions will also be summarized, as will the reasons for dose adjustments.

Adverse events will be reported using MedDRA. Investigators will report a verbatim AE term and a CTCAE v4.0 term and severity for all AEs. For analysis purposes, the following process will be used:

- The CTCAE v4.0 term reported by the investigator will be mapped to the MedDRA Preferred Term (PT) and SOC using the corresponding MedDRA Lower Level Term (LLT), unless the reported CTCAE term is ‘Other – specify.’
- If the reported CTCAE term is ‘Other – specify,’ the MedDRA LLT, PT, and SOC centrally mapped from the verbatim AE term will be used.
- All listings and summaries will use the PT resulting from this process.

Preexisting conditions are defined as AEs that begin prior to the first dose of study drug.

A TEAE is defined as an event that first occurred or worsened in severity after baseline. Comparisons of preexisting conditions to on-treatment events at the LLT level will be used in the treatment-emergent computation.

The following summaries will be produced by PT within SOC: preexisting conditions, SAEs, TEAEs, drug-related TEAEs, and procedure-related TEAEs.

The following summaries will be produced by PT within SOC and maximum CTCAE grade: laboratory-based TEAEs, nonlaboratory-based TEAEs, drug-related laboratory-based TEAEs, and drug-related nonlaboratory-based TEAEs.

Reasons for death will be summarized separately for on-therapy and within 30 days of treatment discontinuation.

Hospitalizations and transfusions during the study treatment period or during the 30-day short-term follow-up period will be summarized by treatment group.

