#### 6.1.2. Definitions and Conventions

**Study drug** refers to abemaciclib or placebo.

**Study treatment** refers to study drug plus NSAID/fulvestrant.

The **date of randomization** is the date the patient was randomly assigned to study treatment using the interactive web response system (IWRS).

The **date of first dose** is the date of the first dose of study drug or NSAID/fulvestrant.

The **baseline value of a safety assessment** is the last value observed prior to the first dose of study drug or NSAI/fulvestrant.

The **baseline value of an efficacy assessment** is the last value observed prior to the date of randomization. If a patient's first assessment occurs after randomization but prior to the first dose, this assessment will be used as the baseline.

The **study day of a safety event or assessment** will be calculated as:

- the difference between the date of the event or assessment and the date of first dose plus 1 for all events or assessments occurring on or after the day of first dose. For example, if an event occurs on 08JUN2014 and the date of first dose was 06JUN2014, the study day of the event is 3.
- the difference between the date of the event or assessment and the date of first dose for all events or assessments occurring before the day of first dose. For example, if an event occurs on 05JUN2014 and the date of first dose was 06JUN2014, the study day of the event is -1.

The **study day of an efficacy event or assessment** will be calculated as:

- the difference between the date of the event or assessment and the date of randomization plus 1 for all events or assessments occurring on or after the date of randomization.
- the difference between the date of the event or assessment and the date of randomization for all events or assessments occurring before the date of randomization.

One **month** is defined as 365/12 days.

Unless otherwise noted, **summaries of continuous variables** will include a mean, median, standard deviation, minimum, and maximum.

Unless otherwise noted, **summaries of categorical variables** will include the frequency and percentage (relative to the population being analyzed) of each category.

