### **6.10.2. Adverse Events**

Adverse event (AE) terms and severity grades will be assigned by the investigator using Common Terminology Criteria for Adverse Events (CTCAE) Version 4. In addition, AE verbatim text will also be mapped by the sponsor or designee to corresponding terminology within MedDRA. Adverse events will be reported using the following reporting process:

- The CTCAE Version 4 term reported by the investigator will be mapped to the MedDRA PT and system organ class (SOC) of the corresponding MedDRA lower level term (LLT), unless the reported CTCAE term is 'Other – specify'.
- If the reported CTCAE term is 'Other – specify' the MedDRA LLT, PT and SOC mapped from the verbatim AE term will be used.
- All listings and summaries will use the PT resulting from this process.

Pre-existing conditions are defined as AEs that begin prior to the first dose of study drug.

A treatment emergent adverse event (TEAE) is defined as any AE that begins on or after the day of first dose or any pre-existing condition that increases in CTCAE grade on or after the day of first dose. Comparisons of pre-existing conditions to on-treatment events at the LLT level will be used in the treatment-emergent computation.

A serious adverse event (SAE) is any AE during this study that results in one of the following outcomes:

- death
- initial or prolonged inpatient hospitalization
- a life-threatening experience (that is, immediate risk of dying)
- persistent or significant disability/incapacity
- congenital anomaly/birth defect
- considered significant by the investigator for any other reason.

Important medical events that may not result in death, be life-threatening, or require hospitalization may be considered SAEs when, based on appropriate medical judgment, they may jeopardize the patient and may require medical or surgical intervention to prevent one of the outcomes listed in this definition.

AE will also be classified based on the relationship to the study treatment.

The following TEAE/SAE listings and summaries will be produced:

- Overview of TEAEs
- Summary of TEAEs by PT (all grade and grade  $\geq 3$ )
- Summary of TEAEs by SOC and PT (all grade and grade  $\geq 3$ )
- Summary of TEAEs by PT and maximum grade (1-5)
- List of SAEs
- Summary of SAEs by SOC and PT (all grade and grade  $\geq 3$ ).

The four summaries will be produced for all TEAEs/SAEs and repeated for TEAEs/SAEs related to study treatment.

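### TEAEs and SAEs are summarised only as patient counts and percentages, with no time-at-risk analysis, although the arms may be observed for adverse events for different lengths of time

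*SAP*

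**What the plan says.** - SAP 6.10.2 lists the AE output: an overview of TEAEs, summaries by preferred term and by organ class, "Summary of TEAEs by PT and maximum grade (1-5", a list of SAEs and an SAE summary. These are repeated for treatment-related events.
- SAP 6.1.2 sets the form of categorical summaries: they "will include the frequency and percentage (relative to the population being analyzed) of each category".
- Protocol 12.2.12 has the same kind of list: "The following summaries will be produced by PT within SOC: preexisting conditions, SAEs, TEAEs, drug-related TEAEs, and procedure-related TEAEs". It adds summaries by maximum grade, but no rate, time-to-event or cumulative-incidence analysis of AEs.
- SAP 6.10.1 uses days on treatment to derive dose intensity, not as a denominator for AEs. SAP 6.15 adds numbers at risk and event counts for the registry, but no person-time.
- A TEAE is "any AE that begins on or after the day of first dose", or a pre-existing condition that worsens from that day (SAP 6.10.2). The SAP states no end to this window. The end comes from collection: Protocol Table JPBQ.10.3 collects all AEs and SAEs during treatment and the "30-day short-term postdiscontinuation follow-up". After that, only SAEs related to study drug or protocol procedures are collected, through long-term follow-up.
- Treatment continues until progression or another discontinuation criterion (Protocol Synopsis and 7.3.2). On PFS, Protocol 12.1 says that with a 14.4-month placebo median, "the hazard ratio of 0.626 amounts to an approximately 8.6-month (59.7%) improvement in median PFS for the abemaciclib plus NSAI arm".
- Safety and tolerability is a comparative secondary objective (Protocol 6.2, SAP 4.2).

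**The concern.** A crude percentage measures the event rate and the length of observation together. If one arm stays on treatment longer because the drug delays progression, it has more time to record events, and a steadily accruing event can look more frequent there at the same underlying rate. If toxicity instead shortens treatment on abemaciclib, the same table can hide a true excess.

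Venous thromboembolism is the obvious example. Protocol 10.3.3.3 reports from other Phase 3 trials that "there was a greater number of patients who experienced VTEs in the abemaciclib plus endocrine therapy arm than in the placebo plus endocrine therapy arm", which is itself a count of patients without time at risk. This trial's planned tables would give the same kind of comparison. The DMC also receives TEAE and SAE summaries at the interim (SAP 6.13).

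SAEs have a second problem. Unrelated SAEs stop being collected about 30 days after study drug stops, while related SAEs can enter the count until death or study completion. One SAE percentage therefore mixes two windows.

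**Working it through.** **Inputs from the documents.** Cohort A: 200 versus 100 patients, placebo median PFS 14.4 months, hazard ratio (HR) 0.626, exponential PFS, analyses at 119 and 170 events (Protocol 12.1, 12.2.6). AE tail of 30 days, with one month = 365/12 days (SAP 6.1.2), so τ = 30/30.42 = 0.99 month.

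**Assumed, because the documents give no figure.** AE rates, constant over time and equal in both arms; accrual pattern; rate of stopping for toxicity. The base case stops treatment only at progression.

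**1. The plan's own figures reproduce.** 14.4/0.626 = 23.0 months, a gain of 8.6 months (59.7%). Censoring is 1 − 170/300 = 43.3%. A two-look calculation with boundaries 0.0082 at 119 events and 0.0223 at 170 gives 81.4% power and an overall one-sided alpha of 0.025.

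**2. Hazards.** Placebo λp = ln 2/14.4 = 0.0481 per month. Abemaciclib λa = 0.626 × 0.0481 = 0.0301 per month.

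**3. Follow-up that yields 170 events** (equal follow-up T for all, the simplest case). With T = 23.7 months: 200 × (1 − e^(−0.0301×23.7)) + 100 × (1 − e^(−0.0481×23.7)) ≈ 102 + 68 = 170.

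**4. Mean AE window** = τ + (1 − e^(−λ(T−τ)))/λ, with the tail cut at data cut-off.
- Abemaciclib: 0.99 + 16.4 = 17.4 months.
- Placebo: 0.99 + 13.8 = 14.8 months.
- Ratio 1.18. Uniform accrual over 12 to 24 months gives 17.4–17.5 versus 14.7–14.8 months, ratio 1.18–1.19.
- At 119 events the ratio is 1.10 with equal follow-up and about 1.12 with 18-month accrual.

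**5. Crude percentage at equal rate h** = 1 − e^(−hτ) + h·e^(−hτ)·(1 − e^(−(λ+h)(T−τ)))/(λ+h).

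| h per month | Abemaciclib | Placebo | Difference (points) | Ratio | SE of difference (points) |
|---|---|---|---|---|---|
| 0.01 | 15.7% | 13.5% | 2.3 | 1.17 | 4.3 |
| 0.02 | 28.5% | 24.6% | 3.9 | 1.16 | 5.4 |
| 0.04 | 47.5% | 41.6% | 5.9 | 1.14 | 6.1 |
| 0.10 | 75.4% | 68.4% | 6.9 | 1.10 | 5.6 |

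Differences are taken before rounding. SE = √(p1(1−p1)/200 + p2(1−p2)/100). With accrual spread over 12 to 24 months, the ratio for 0.01 to 0.04 per month runs from 1.14 to 1.18. It falls as events become common, and is small for events that start early in treatment, when both arms are still under observation.

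**6. Stopping for toxicity.** Add a hazard k of stopping on abemaciclib only. The windows are equal when λa + k = λp, so k = 0.0481 − 0.0301 = 0.0180 per month, or 0.216 per year: 1 − e^(−0.216) = 19% stopping in 12 months. At 26% in 12 months (k = −ln 0.74/12 = 0.0251) the window ratio falls to 0.94 with 18-month accrual.

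**7. With time at risk as denominator**, the equal-rate case gives a rate ratio of 1.00 by construction, on about 290 patient-years (17.4 × 200/12) versus 123 (14.8 × 100/12).

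**The case against.** The best case for the plan has four parts.

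- **Stopping is not only for progression.** Protocol 7.3.2 also lists unacceptable toxicity, need for a third dose reduction, and investigator or patient decision. A reader might infer that the design guarantees longer observation on abemaciclib, so that an equal rate must show as excess harm. The documents do not support that: they give no rate of stopping for toxicity, and step 6 shows that a plausible one removes or reverses the gap. This limits the claim, but it also means that the direction of the distortion is unknown in advance.
- **The distortion is modest.** It is about 0.5 to 1 standard error for rates of 0.01 to 0.04 per month, and no between-arm AE test is planned. A reader might take the 59.7% gain in median PFS as the size of the inflation. That ignores the data cut-off. Nor is the relative gap of about 15% to 16% in mean windows the share of abemaciclib events falling after the mean placebo window; about 30% of abemaciclib person-time lies there.
- **Other outputs help.** Exposure by cycle and cumulatively (SAP 6.10.1), cycles completed (Protocol 12.2.12), laboratory grades by cycle (SAP 6.10.4) and registry event counts (SAP 6.15) are planned, and further exploratory analyses are allowed. So it would be wrong to say that the trial could never separate longer observation from excess risk: the data exist. What is missing is a pre-specified analysis that joins AEs to exposure.
- **The SAP does not set a 30-day limit.** A reader might attribute one to its TEAE definition. The limit is the protocol's collection rule, and it does not apply to related SAEs.

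All four parts stand as limits on size and wording. None supplies the missing analysis.

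**Conclusion.** The gap is real and moderate. For a comparative safety objective, the plan pre-specifies no AE analysis that uses time at risk, it leaves the TEAE window without a stated end, and its SAE counts mix two collection windows.

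On the plan's PFS assumptions, and if progression drives stopping, the Cohort A windows differ by a ratio of about 1.18 to 1.19 at the final analysis. An equal constant rate of 0.01 to 0.04 per month can then show as a crude relative risk of about 1.14 to 1.18. The size rests on exponential PFS, constant equal AE rates, assumed accrual and no stopping for toxicity. With about 20% abemaciclib-only toxicity stopping in the first year the gap is nil, and beyond that it reverses. The planned exposure tables can indicate the direction of the gap, but no AE table corrects for it. The primary efficacy inference is unaffected.

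**What to change.** In SAP 6.10.2, keep the crude tables and add beside them, by arm within each cohort, for any TEAE, Grade 3 or higher TEAE, SAE, VTE and the frequent preferred terms:

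- first events per 100 patient-years at risk, counting time from first dose to the first event or the end of the window;
- cumulative incidence of the first event at 6 and 12 months (Aalen-Johansen, death as the competing event);
- between-arm differences with 95% confidence intervals.

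State that the TEAE window ends at the close of the 30-day follow-up or at data cut-off, whichever is earlier. Apply the same window to the main SAE tables, and report related SAEs arising later in a separate table.

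The cost is SAP wording and a few more tables, built from onset and dosing dates that the TEAE and exposure derivations already need. Conduct, data collection, alpha and sample size do not change. Two limitations should be written into the SAP. The rate assumes a constant hazard. The cumulative incidence does not, but it treats leaving the AE window after stopping treatment as non-informative censoring, which is doubtful when toxicity is the reason for stopping.

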### **6.10.3. Deaths**

All deaths on study not attributed to study disease by the investigator will be listed along with the reason for death, if known. For those deaths attributed to an AE, the listing will include the PT of the AE. A summary of deaths including reasons for death will be produced.

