Patients in Cohort B will be randomized using the following stratification factors: nature of disease (visceral metastases vs. non-visceral metastases) and sensitivity to endocrine therapy (primary resistance vs. secondary resistance). The presence of visceral metastases refers to lung, liver, pleural, or peritoneal, or adrenal gland involvement at the time of randomization. Primary clinical resistance to endocrine therapy is defined as follows: 1) for endocrine therapy in the adjuvant setting, recurrence within the first 2 years of adjuvant endocrine therapy while on endocrine therapy, or 2) for endocrine therapy in the locoregionally recurrent or metastatic setting, progression within first 6 months of initiating first-line endocrine therapy while on endocrine therapy. Patients receiving prior endocrine therapy who do not meet the definition of primary clinical resistance will be considered to have secondary clinical resistance.

The primary analysis of the PFS endpoint will occur after approximately 170 PFS events have been observed in Cohort A. An interim analysis will be conducted after approximately 119 PFS events are observed to provide early efficacy information and allow for potential early communication with regulatory agencies. (see Section 12.2.6 for details).

The interim analysis of Cohort B will follow the timeline of Cohort A, which will occur only if the interim of Cohort A turns out to be positive. If patients in Cohort A continue being followed for PFS until final analysis, the final analysis of Cohort B will be conducted at the same time of Cohort A final analysis. If Cohort A stops early at interim due to efficacy, the final analysis of Cohort B may be conducted after approximately 105 PFS events have been observed in Cohort B. (see Section 12.2.14 for details).

For each cohort, all patients will be followed for progression and survival information until death or study completion, whichever occurs first.

Terms used to describe the periods during the study are defined below:

- **Baseline:** begins when the informed consent form (ICF) is signed and ends at the first study treatment dose (or at discontinuation, if no treatment is given). This may be up to 28 days prior to the first study treatment dose.
- **Study Period:** begins at the first study treatment and ends at study completion. The study period does not include the continued access period.

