#### **10.3.1.1. Serious Adverse Events**

All AEs occurring after signing the ICF are recorded in the eCRF and assessed for serious criteria. An SAE is any AE from this study that results in 1 of the following outcomes:

- death
- a life-threatening experience (ie, immediate risk of dying)
- persistent or significant disability/incapacity
- initial or prolonged inpatient hospitalization
- congenital anomaly/birth defect
- considered significant by the investigator for any other reason

Important medical events that may not result in death, be life-threatening, or require hospitalization may be considered serious adverse drug events when, based upon appropriate medical judgment, they may jeopardize the patient and may require medical or surgical intervention to prevent one of the outcomes listed in this definition.

Serious adverse event collection begins after the patient has signed informed consent and has received study drug. If a patient experiences an SAE after signing informed consent, but prior to receiving study drug, the event will not be reported as serious unless the investigator feels the event may have been caused by a protocol procedure.

Data on SAEs that occur before the end of trial will be stored in the collection database and the Lilly Safety System.

Study site personnel must alert Lilly or its designee of any SAE within 24 hours of investigator awareness of the event via a sponsor-approved method. If study site personnel contact Lilly or its designee by telephone regarding an SAE, study site personnel must also immediately provide official notification on study-specific SAE forms.

This 24-hour notification requirement refers to the initial SAE information and all follow-up SAE information.

Planned surgeries should not be reported as SAEs unless the underlying medical condition has worsened during the course of the study.

Planned hospitalizations or procedures for preexisting conditions that are already recorded in the patient's medical history at the time of study enrollment should not be considered SAEs. Hospitalization or prolongation of hospitalization without a precipitating clinical AE (eg, for the administration of study treatment or other protocol-required procedure) should not be considered SAEs.

Serious adverse events due to disease progression, including death, should not be reported unless the investigator deems them to be possibly related to the study drug.

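### SAP 6.10.3 omits the protocol's on-therapy and 30-day split of reasons for death and lists no death attributed to study disease, so an early death put down wholly to progression has no patient-level safety listing

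*SAP*

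**What the plan says.** Protocol 12.2.12 (Safety Analyses) specifies the output: "Reasons for death will be summarized separately for on-therapy and within 30 days of treatment discontinuation".

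SAP 6.10.3 (Deaths) specifies two outputs. The listing is restricted: "All deaths on study not attributed to study disease by the investigator will be listed", with the reason where it is known. The summary covers all deaths and names no time window: "A summary of deaths including reasons for death will be produced".

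Protocol 10.3.1.1 restricts what reaches the SAE data: "Serious adverse events due to disease progression, including death, should not be reported unless the investigator deems them to be possibly related" to study drug.

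SAP 6.10.2 supplies the other routes by which a death can be seen. It counts death among the SAE outcomes and plans a list of SAEs and a table of treatment-emergent events by preferred term and maximum grade, with Grade 5 included. SAP 6.7.2.2 analyses overall survival, which counts deaths from any cause. Protocol 8.1 sets the length of follow-up: "all patients will be followed for progression and survival information until death or study completion, whichever occurs first". Deaths on study therefore include those in long-term follow-up.

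**The concern.** Deaths on treatment or shortly after it are the ones most likely to reveal fatal toxicity. In advanced cancer, a fatal embolic, hepatic or infectious event can be mistaken for progression. The protocol gives reason to look: section 10.3.3.3 records more venous thromboembolic events with abemaciclib in the Phase 3 breast cancer studies, and amendment (e) added hepatic monitoring. A table of deaths by arm and window is a check that does not depend on the investigator's causal judgement. The protocol asked for the windows and SAP 6.10.3 does not provide them.

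The listing makes this worse. The death listing and the SAE exemption turn on the same judgement, so one attribution to progression closes both patient-level routes at once.

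**Working it through.** The plan states no figure to reproduce here. The check is a comparison of the texts, followed by an illustration of size.

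**Step 1. Is the split carried over?** Protocol 12.2.12 names two windows. SAP 6.10.3 names none, and a single unsplit table would satisfy it as written. Protocol 12.2.1 provides for modifications to be described and justified in the SAP. The SAP's revision history (section 3) mentions no change to the analysis of deaths, and no justification appears elsewhere. The split is neither repeated nor withdrawn.

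**Step 2. Where does each kind of early death appear?**

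| Early death | Death listing (SAP 6.10.3) | SAE list (SAP 6.10.2) | Grade 5 TEAE table (SAP 6.10.2) | Death summary, no window | OS |
|---|---|---|---|---|---|
| Not attributed to disease, fatal AE reported | Yes | Yes | Yes, if treatment-emergent | Yes | Yes |
| Attributed to disease, but a fatal AE reported (e.g. possibly related) | No | Yes | Yes, if treatment-emergent | Yes | Yes |
| Attributed wholly to progression, no SAE reported | No | No | No | Yes | Yes |

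Only the third row lacks a patient-level safety record, and that row is what Protocol 10.3.1.1 instructs sites to produce.

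**Step 3. How far could an unwindowed summary dilute early deaths?** The documents give no death counts by window, so this is illustration only.

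- Inputs from the documents: 450 patients (Protocol 12.1); median OS of 2 to 3 years for metastatic breast cancer generally (Protocol 5), taken as 24 to 36 months.
- Assumed: exponential survival, mean follow-up of 18 to 30 months, and 1% to 5% of patients dying on therapy or within 30 days (4.5 to 22.5 patients).
- Formula: expected deaths = 450 × (1 − exp(−ln 2 × follow-up / median OS)).
- Fewest deaths, 36-month median and 18 months of follow-up: 450 × (1 − exp(−0.347)) = about 132.
- Most deaths, 24-month median and 30 months of follow-up: 450 × (1 − exp(−0.866)) = about 261.
- Early deaths as a share of all deaths: from 4.5/261 = 1.7% to 22.5/132 = 17%.

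**Step 4. What would windowing show?** Suppose early deaths in Cohort A were 6/200 against 1/100 (assumed), a difference of 2 points. Suppose also that 37% to 50% of the cohort had died overall (assumed). The standard error of the difference in total death proportions is sqrt(p(1−p)(1/200 + 1/100)), or 5.9 to 6.1 points. Within the window it is sqrt(0.03×0.97/200 + 0.01×0.99/100) = 1.6 points, so z = 2/1.6 = about 1.3, and Fisher's two-sided p = 0.43. Windowing makes such a pattern visible. It would not establish it.

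**The case against.** The strongest reply is that nothing has been lost. The protocol's split is still in force, because the SAP does not withdraw it and silence is not a rule to pool. That stands as a point about authority. It does not cure the SAP, which is the document that defines the outputs and would not prompt anyone to produce two windows.

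A reader might infer that fatal toxicity labelled as disease appears in no listing at all. The documents do not support that. Protocol Table JPBQ.10.3 collects all AEs and SAEs on treatment and for 30 days afterwards. The exemption covers only events due to progression and lapses once a drug relationship is thought possible. Protocol 10.3.1 classes even an undetermined relationship as related. A fatal event reported under these rules reaches the SAE list.

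A reader might also infer that the SAP outputs cannot show a mortality imbalance between arms. That is too strong: Grade 5 events are tabulated by arm, and OS counts every death. OS is timed from randomisation rather than last dose, so it does not fully replace a windowed table.

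A third tempting reading is that early deaths are swamped by late ones. The summary is by reason, which already separates AE deaths from disease deaths, and the dilution figures are assumptions. The 24-month median OS also sits poorly with the design: Protocol 12.1 implies a median PFS of 14.4/0.626 = 23.0 months on abemaciclib plus NSAI, leaving about one month between median PFS and median OS.

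Finally, the protocol requires no death listing, so listing all early deaths goes beyond it. That is true. The proposal rests on the attribution filter being a stated rule with a foreseeable blind spot, not on a protocol breach.

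**Conclusion.** The point holds in a limited form. Two facts follow from the text without assumptions: SAP 6.10.3 does not carry over the two windows in Protocol 12.2.12, and its listing excludes every death attributed to study disease. Taken with Protocol 10.3.1.1, an early death attributed wholly to progression with no SAE reported has no patient-level safety listing. It survives only as a count in an unwindowed summary and as an event in OS.

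The number of such deaths cannot be derived from the documents. The 1.7% to 17% share is a range under assumed follow-up, survival and early-death rates, and the conclusion does not depend on it. Alpha, power and the primary analysis are unaffected. This is a safety-reporting gap that should be closed before the final outputs are programmed.

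**What to change.** Amend SAP 6.10.3 in two respects.

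- Summarise deaths and their reasons by arm within cohort in the protocol's two windows: on therapy, and within 30 days of treatment discontinuation.
- List every death in those windows regardless of attribution, with the investigator's stated reason, time since last dose and any associated AE term. The restricted listing may stay for later deaths.

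The inputs (reason for death, dosing and discontinuation dates, AE records) are already planned data. The cost is SAP wording, one re-cut table and a somewhat longer listing, with no effect on sites, design or error rates. The change does not alter the SAE reporting rule in Protocol 10.3.1.1. It provides a view of early deaths that does not depend on that rule.
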